6.7.3. Management of Virologic Rebound (Open-Label B/F/TAF Rollover Extension)

[figure not shown]
- If the viral load is ≥ 50 copies/mL, HIV-1 RNA should be repeated at a scheduled or unscheduled visit (2-3 weeks after the date of the original test with HIV-1 RNA ≥ 50 copies/mL).
- Upon confirmation of HIV-1 RNA ≥ 50 copies/mL, potential causes of virologic failure should be documented. Assessments should include:
 - Adherence
 - Concomitant medication
 - Comorbidities (for example: active substance abuse, depression, other intercurrent illnesses)
- If virologic rebound is confirmed, and the HIV-1 RNA is < 200 copies/mL, subjects may remain on their current regimen at the discretion of the Investigator. Subject will return for a repeat within 2-3 weeks.
- If virologic failure is confirmed at the scheduled or unscheduled visit and HIV-1 RNA value is ≥ 200 copies/mL, the blood samples from the confirmation visit will be used for HIV-1 genotype/phenotype testing.
- If genotype/phenotype resistance to study drug is documented, study drugs should be discontinued.
- If no resistance is detected from genotype/phenotype testing, subject may remain on study drug and HIV-1 RNA should be repeated (2-3 weeks from the date of confirmed test with HIV-1 RNA ≥ 50 copies/mL). Investigators should carefully evaluate the benefits and risks of remaining on study drug for each individual subject and document this assessment in the subject's source documents. Investigators who opt to discontinue study drugs for an individual subject must discuss with the Medical Monitor prior to study drug discontinuation.

6.7.4. Subjects with ≥ 200 copies/mL of HIV-1 in the Absence of VR

Subjects with HIV-1 RNA < 50 copies/mL could subsequently experience unconfirmed blips of HIV-1 RNA ≥ 200 copies/mL. Such subjects will be analyzed for resistance if the unconfirmed rebound happens at the last visit while receiving study drugs (or within 72 hours of discontinuation of study treatment).

Please refer to [Figure 6-1](#) for the management of subjects who meet the criteria for virologic failure.

Figure 6-2. Virologic Rebound Schema (Open-Label B/F/TAF Rollover Extension)

- a If virologic rebound is not confirmed, the subject will remain on their current regimen.
- b If virologic rebound is confirmed and the HIV-1 RNA is ≥ 200 copies/mL, the HIV-1 genotype and phenotype (reverse transcriptase, protease and integrase) will be analyzed.
- c Based on the results of the genotypic and phenotypic assays, the subject will remain on study drugs or study drugs will be discontinued. If genotyping or phenotyping assays fail, a new ARV regimen may be configured at the discretion of the Investigator.
- d If no resistance is detected, HIV-1 RNA will be repeated (2-3 weeks later). Investigator reviews study drug continuation/discontinuation options and discuss with the Medical Monitor prior to study drug discontinuation
- e A new ARV regimen will be configured, at the Investigator's discretion, and the subject will remain in the study.

7. ADVERSE EVENTS AND TOXICITY MANAGEMENT

7.1. Definitions of Adverse Events, Adverse Reactions, and Serious Adverse Events

7.1.1. Adverse Events

An adverse event (AE) is any untoward medical occurrence in a clinical study subject administered a medicinal product, which does not necessarily have a causal relationship with the treatment. An AE can therefore be any unfavorable and/or unintended sign, symptom, or disease temporally associated with the use of a medicinal product, whether or not considered related to the medicinal product. AEs may also include pre- or post-treatment complications that occur as a result of protocol specified procedures, lack of efficacy, overdose, drug abuse/misuse reports, or occupational exposure. Preexisting events that increase in severity or change in nature during or as a consequence of participation in the clinical study will also be considered AEs.

An AE does not include the following:

- Medical or surgical procedures such as surgery, endoscopy, tooth extraction, and transfusion. The condition that led to the procedure may be an adverse event and must be reported.
- Pre-existing diseases, conditions, or laboratory abnormalities present or detected before the Screening Visit that do not worsen
- Situations where an untoward medical occurrence has not occurred (e.g., hospitalization for elective surgery, social and/or convenience admissions)
- Overdose without clinical sequelae (see Section [7.5](#))
- Any medical condition or clinically significant laboratory abnormality with an onset date before the consent form is signed and not related to a protocol-associated procedure is not an AE. It is considered to be pre-existing and should be documented on the medical history CRF.

7.1.2. Serious Adverse Events

A **serious adverse event** (SAE) is defined as an event that, at any dose, results in the following:

- Death
- Life-threatening (Note: The term “life-threatening” in the definition of “serious” refers to an event in which the subject was at risk of death at the time of the event; it does not refer to an event that hypothetically might have caused death if it were more severe.)
- In-patient hospitalization or prolongation of existing hospitalization
- Persistent or significant disability/incapacity

- A congenital anomaly/birth defect
- A medically important event or reaction: such events may not be immediately life-threatening or result in death or hospitalization but may jeopardize the subject or may require intervention to prevent one of the other outcomes constituting SAEs. Medical and scientific judgment must be exercised to determine whether such an event is a reportable under expedited reporting rules. Examples of medically important events include intensive treatment in an emergency room or at home for allergic bronchospasm; blood dyscrasias or convulsions that do not result in hospitalization; and development of drug dependency or drug abuse. For the avoidance of doubt, infections resulting from contaminated medicinal product will be considered a medically important event and subject to expedited reporting requirements.

7.1.3. Clinical Laboratory Abnormalities and Other Abnormal Assessments as Adverse Events or Serious Adverse Events

Laboratory abnormalities without clinical significance are not recorded as AEs or SAEs. However, laboratory abnormalities (e.g., clinical chemistry, hematology, and urinalysis) that require medical or surgical intervention or lead to study drug interruption, modification, or discontinuation must be recorded as an AE, as well as an SAE, if applicable. In addition, laboratory or other abnormal assessments (e.g., electrocardiogram, x-rays, vital signs) that are associated with signs and/or symptoms must be recorded as an AE or SAE if they meet the definition of an AE or SAE as described in Sections 7.1.1 and 7.1.2. If the laboratory abnormality is part of a syndrome, record the syndrome or diagnosis (e.g., anemia), not the laboratory result (i.e., decreased hemoglobin).

For specific information on handling of clinical laboratory abnormalities in this study, please refer to Section 7.6.

7.2. Assessment of Adverse Events and Serious Adverse Events

The investigator or qualified sub-investigator is responsible for assessing AEs and SAEs for causality and severity, and for final review and confirmation of accuracy of event information and assessments.

7.2.1. Assessment of Causality for Study Drugs and Procedures

The investigator or qualified sub-investigator is responsible for assessing the relationship to study drug using clinical judgment and the following considerations:

- **No:** Evidence exists that the adverse event has an etiology other than the study drug. For SAEs, an alternative causality must be provided (e.g., pre-existing condition, underlying disease, intercurrent illness, or concomitant medication).
- **Yes:** There is reasonable possibility that the event may have been caused by the investigational medicinal product.

It should be emphasized that ineffective treatment should not be considered as causally related in the context of adverse event reporting.

The relationship to study procedures (e.g., invasive procedures such as venipuncture or biopsy) should be assessed using the following considerations:

- **No:** Evidence exists that the adverse event has an etiology other than the study procedure.
- **Yes:** The adverse event occurred as a result of protocol procedures, (e.g., venipuncture)

7.2.2. Assessment of Severity

Severity should be recorded and graded according to the GSI Grading Scale for Severity of Adverse Events and Laboratory Abnormalities ([Appendix 6](#)) For adverse events associated with laboratory abnormalities, the event should be graded on the basis of the clinical severity in the context of the underlying conditions; this may or may not be in agreement with the grading of the laboratory abnormality.

7.3. Investigator Requirements and Instructions for Reporting Adverse Events and Serious Adverse Events to Gilead

Requirements for collection prior to study drug initiation:

After informed consent, but prior to initiation of study drug, the following types of events should be reported on the case report form (eCRF): all SAEs and adverse events related to protocol-mandated procedures.

7.3.1. Adverse Events

Following initiation of study drug, collect all AEs, regardless of cause or relationship, until 4 weeks after last administration of study drug must be reported to the eCRF database as instructed.

All AEs should be followed up until resolution or until the adverse event is stable, if possible. Gilead Sciences may request that certain AEs be followed beyond the protocol defined follow up period.

7.3.2. Serious Adverse Events

All SAEs, regardless of cause or relationship, that occur after the subject first consents to participate in the study (i.e., signing the informed consent) and throughout the duration of the study, including the protocol-required post treatment follow-up period, must be reported to the eCRF database and Gilead Pharmacovigilance and Epidemiology (PVE) as instructed. This also includes any SAEs resulting from protocol-associated procedures performed after informed consent is signed.

Any SAEs and deaths that occur after the post treatment follow-up visit but within 30 days of the last dose of study drug, regardless of causality, should also be reported.

All SAEs should be followed up until resolution if possible. If by the last day on study (including the off-study drug follow-up period) the SAE has not resolved, then the SAE will be followed up until the investigator and/or Gilead Sciences determine that the subject's condition is stable. However, Gilead Sciences may request that certain SAEs be followed until resolution.

Investigators are not obligated to actively seek SAEs after the protocol defined follow up period, however, if the investigator learns of any SAEs that occur after study participation has concluded and the event is deemed relevant to the use of study drug, he/she should promptly document and report the event to Gilead PVE.

- All AEs and SAEs will be recorded in the eCRF database within the timelines outlined in the eCRF completion guideline.

Serious Adverse Event Paper Reporting Process

- Serious Adverse Event Paper Reporting Process (only to be used if EDC System is not available)
 - All SAEs will be recorded on the serious adverse event report form and submitted by faxing the report form within 24 hours of the investigator's knowledge of the event to the attention of:

Gilead Sciences PVE: [contact]
E-mail: [contact]

Electronic Serious Adverse Event (eSAE) Reporting Process

- Site personnel record all SAE data in the eCRF database and from there transmit the SAE information to Gilead PVE within 24 hours of the investigator's knowledge of the event. Detailed instructions can be found in the eCRF completion guidelines.
 - If the SAE was reported via paper, it must be transcribed into the eCRF Database according to instructions in the eCRF completion guidelines.
 - If an SAE has been reported via a paper form because the eCRF database has been locked, no further action is necessary.
 - For fatal or life-threatening events, copies of hospital case reports, autopsy reports, and other documents are also to be submitted by e-mail or fax when requested and applicable. Transmission of such documents should occur without personal subject identification, maintaining the traceability of a document to the subject identifiers.

- Additional information may be requested to ensure the timely completion of accurate safety reports.
- Any medications necessary for treatment of the SAE must be recorded onto the concomitant medication section of the subject's eCRF and the event description section of the SAE form.

7.4. Gilead Reporting Requirements

Depending on relevant local legislation or regulations, including the applicable US FDA Code of Federal Regulations, the EU Clinical Trials Directive (2001/20/EC) and relevant updates, and other country-specific legislation or regulations, Gilead may be required to expedite to worldwide regulatory agencies reports of SAEs, serious adverse drug reactions (SADRs), or suspected unexpected serious adverse reactions (SUSARs). In accordance with the EU Clinical Trials Directive (2001/20/EC), Gilead or a specified designee will notify worldwide regulatory agencies and the relevant IEC in concerned Member States of applicable SUSARs as outlined in current regulations.

Assessment of expectedness for SAEs will be determined by Gilead using reference safety information specified in the investigator's brochure or relevant local label as applicable.

All investigators will receive a safety letter notifying them of relevant SUSAR reports associated with the study drug. The investigator should notify the IRB or IEC of SUSAR reports as soon as is practical, where this is required by local regulatory agencies, and in accordance with the local institutional policy.

7.5. Special Situations Reports

7.5.1. Definitions of Special Situations

Special situation reports include all reports of medication error, abuse, misuse, overdose, reports of adverse events associated with product complaints, and pregnancy reports regardless of an associated AE.

Medication error is any unintentional error in the prescribing, dispensing, or administration of a medicinal product while in the control of the health care provider, subject, or consumer.

Abuse is defined as persistent or sporadic intentional excessive use of a medicinal product by a subject.

Misuse is defined as any intentional and inappropriate use of a medicinal product that is not in accordance with the protocol instructions or the local prescribing information.

An overdose is defined as an accidental or intentional administration of a quantity of a medicinal product given per administration or cumulatively which is above the maximum recommended dose as per protocol or in the product labelling (as it applies to the daily dose of the subject in question). In cases of a discrepancy in drug accountability, overdose will be established only

when it is clear that the subject has taken the excess dose(s). Overdose cannot be established when the subject cannot account for the discrepancy except in cases in which the investigator has reason to suspect that the subject has taken the additional dose(s).

Product complaint is defined as complaints arising from potential deviations in the manufacture, packaging, or distribution of the medicinal product.

7.5.2. Instructions for Reporting Special Situations

7.5.2.1. Instructions for Reporting Pregnancies

The investigator should report pregnancies in female study subjects that are identified after initiation of study drug and throughout the study, including the post study drug follow-up period, to Gilead PVE using the pregnancy report form within 24 hours of becoming aware of the pregnancy.

Refer to the eCRF completion guidelines for full instructions on the mechanism of pregnancy reporting.

The pregnancy itself is not considered an AE nor is an induced elective abortion to terminate a pregnancy without medical reasons.

Any premature termination of pregnancy (e.g., a spontaneous abortion, an induced therapeutic abortion due to complications or other medical reasons) must be reported within 24 hours as an SAE. The underlying medical reason for this procedure should be recorded as the AE term.

A spontaneous abortion is always considered to be an SAE and will be reported as described in Section 7.3.2. Furthermore, any SAE occurring as an adverse pregnancy outcome post study must be reported to Gilead PVE.

The subject should receive appropriate monitoring and care until the conclusion of the pregnancy. The outcome should be reported to Gilead PVE using the pregnancy outcome report form. If the end of the pregnancy occurs after the study has been completed, the outcome should be reported directly to Gilead PVE.

Gilead PVE contact information is as follows:

Gilead Sciences PVE:	[contact]
	E-mail:	[contact]

Refer to [Appendix 7](#) for Pregnancy Precautions, Definition for Female of Childbearing Potential, and Contraceptive Requirements.

7.5.2.2. Reporting Other Special Situations

All other special situation reports must be reported on the special situations report form and forwarded to Gilead PVE within 24 hours of the investigator becoming aware of the situation. These reports must consist of situations that involve study drug and/or Gilead concomitant medications, but do not apply to non-Gilead concomitant medications.

Special situations involving non-Gilead concomitant medications does not need to be reported on the special situations report form; however, for special situations that result in AEs due to a non-Gilead concomitant medication, the AE should be reported on the AE form.

Any inappropriate use of concomitant medications prohibited by this protocol should not be reported as “misuse,” but may be more appropriately documented as a protocol deviation.

Refer to the CRF/eCRF completion guidelines for full instructions on the mechanism of special situations reporting.

All clinical sequelae in relation to these special situation reports will be reported as AEs or SAEs at the same time using the AE eCRF and/or the SAE report form. Details of the symptoms and signs, clinical management, and outcome will be reported, when available.

7.6. Toxicity Management

All clinical and clinically significant laboratory toxicities will be managed according to uniform guidelines detailed in [Appendix 5](#) as outlined below.

- All clinically significant Grades 3 and 4 laboratory abnormalities should be repeated within 3 calendar days to confirm toxicity grade. Confirmation of toxicity grade is required prior to the next dose of study drug for any Grade 3 and 4 laboratory abnormality that in the opinion of the Investigator is clinically significant and may pose a risk to the subject’s safety.
- Clinical events and clinically significant laboratory abnormalities will be graded according to the GSI Grading Scale for Severity of Adverse Events and Laboratory Abnormalities (refer to [Appendix 6](#)).
- Any questions regarding toxicity management should be directed to the Medical Monitor.

7.6.1. Grades 1 and 2 Laboratory Abnormality or Clinical Event

Continue study drug at the discretion of the Investigator.

7.6.2. Grade 3 Laboratory Abnormality or Clinical Event

- For Grade 3 clinically significant laboratory abnormality or clinical event, study drug may be continued if the event is considered to be unrelated to study drug.
- For a Grade 3 clinical event, or clinically significant laboratory abnormality confirmed by repeat testing, that is considered to be related to study drug, study drug should be withheld until the toxicity returns to \leq Grade 2.
- If a laboratory abnormality recurs to \geq Grade 3 following re-challenge with study drug and is considered related to study drug, then study drug should be permanently discontinued and the subject managed according to local practice. Recurrence of laboratory abnormalities considered unrelated to study drug may not require permanent discontinuation.

7.6.3. Grade 4 Laboratory Abnormality or Clinical Event

- For a Grade 4 clinical event or clinically significant Grade 4 laboratory abnormality confirmed by repeat testing that is considered related to study drug, study drug should be permanently discontinued and the subject managed according to local practice. The subject should be followed as clinically indicated until the laboratory abnormality returns to baseline or is otherwise explained, whichever occurs first. A clinically significant Grade 4 laboratory abnormality that is not confirmed by repeat testing should be managed according to the algorithm for the new toxicity grade.

Study Drug may be continued without dose interruption for a clinically non-significant Grade 3-4 laboratory abnormality (e.g., CK elevation after strenuous exercise, or triglyceride elevation that is non-fasting or that can be medically managed) or a Grade 3-4 clinical event considered unrelated to study drug.

8. STATISTICAL CONSIDERATIONS

8.1. Analysis Objectives and Endpoints

8.1.1. Analysis Objectives

The primary objective of this study is:

- To evaluate the safety and tolerability of the elvitegravir/cobicistat/emtricitabine/tenofovir alafenamide (EVG/COBI/FTC/TAF; E/C/F/TAF) fixed-dose combination (FDC) in HIV-1 infected adults with end stage renal disease (ESRD) on chronic hemodialysis (HD) at Week 48

The secondary objectives of this study are:

- To evaluate the safety and tolerability of the EVG/COBI/FTC/TAF; E/C/F/TAF FDC in HIV-1 infected adults with ESRD on chronic HD at Week 96
- To evaluate the proportion of subjects receiving E/C/F/TAF FDC with virologic response (HIV-1 RNA < 50 copies/mL, as defined by the FDA Snapshot analysis) at Weeks 24, 48 and 96
- To evaluate plasma pharmacokinetics (PK) of EVG, COBI, FTC, TAF and TFV in HIV-1 infected patients with ESRD on chronic HD
- To evaluate the safety and tolerability of B/F/TAF in HIV-1 infected patients with ESRD on chronic HD

8.1.2. Primary Endpoint

The primary endpoint is the incidence of treatment-emergent grade 3 or higher adverse events up to Week 48 in subjects receiving E/C/F/TAF.

8.1.3. Secondary Endpoints

- Incidence of treatment-emergent grade 3 or higher adverse events up to Week 96 in subjects receiving E/C/F/TAF
- Proportion of subjects receiving E/C/F/TAF with HIV-1 RNA < 50 copies/mL at Weeks 24, 48, and 96 as defined by the FDA snapshot algorithm
- The pharmacokinetics parameters of EVG, COBI, FTC, TAF and TFV, **CCI** [REDACTED]

Similar safety and tolerability measures will be used to characterize the safety and tolerability of B/F/TAF in HIV-1 infected patients with ESRD on chronic HD.

8.2. Analysis Conventions

8.2.1. Analysis Sets

8.2.1.1. Full Analysis Set

Full Analysis Set (FAS): The Full Analysis Set will include all the subjects who were enrolled and received at least one dose of study drug. The FAS will exclude subjects with major protocol violations. The FAS analysis set is the primary analysis set for the efficacy analyses.

There will be 2 FAS: the E/C/F/TAF FAS which includes subjects who received at least one dose of E/C/F/TAF study drug, and the B/F/TAF FAS which includes subjects who received at least one dose of B/F/TAF study drug.

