6. STUDY PROCEDURES

The study procedures to be conducted for each subject enrolled in the study are presented in tabular form in [Appendix 2](#) and described in the text that follows.

The investigator must document any deviation from protocol procedures in the subject's source documents and electronic Case Report Forms (eCRFs). In addition, the Sponsor and the Contract Research Organization (CRO) should be promptly notified of any protocol deviations.

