1. INTRODUCTION

This statistical analysis plan (SAP) describes the statistical analysis methods and data presentations to be used in tables, figures, and listings (TFLs) of the final analysis for Study GS-US-292-1825, which will be performed when all subjects have completed the study or prematurely discontinued from the study. This SAP is based on the study Protocol Amendment 2.1, dated 01 May 2018, and electronic case report form (eCRF). The SAP will be finalized before database finalization. Any changes made to the analyses after the finalization of the SAP will be documented in the final clinical study report. Analyses that were performed as part of interim clinical study reports will not be repeated for the final analysis unless otherwise specified.

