3.1.3. E/C/F/TAF Full Analysis Set

The **E/C/F/TAF Full Analysis Set (FAS)** will include all subjects who (1) were enrolled in the study and (2) received at least 1 dose of E/C/F/TAF study drug. This is the primary analysis set for the E/C/F/TAF efficacy analyses.

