3.1.4. B/F/TAF Full Analysis Set

The **B/F/TAF Full Analysis Set (FAS)** will include all subjects who (1) were enrolled in the study and (2) received at least 1 dose of B/F/TAF study drug. This is the primary analysis set for the B/F/TAF efficacy analyses.

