4.3. Protocol Deviations

A listing will be provided for subjects in the All Enrolled Subjects analysis set who violated at least 1 inclusion or exclusion criterion. The listing will include the criteria not met.

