7. EFFICACY ANALYSES

The proportions of subjects with HIV-1 RNA < 50 copies/mL at Weeks 24 and 48 as defined by the US FDA-defined snapshot algorithm were summarized as part of the Week 48 clinical study report and will not be repeated for the final analysis.

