7.3. Changes From Protocol-Specified Efficacy Analyses

There are no changes from the protocol-specified efficacy analyses.

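### Does the protocol's exclusion of major violators from the Full Analysis Set, which the SAP omits, put the efficacy results at risk?

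*Protocol*

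**What the plan says.** Protocol 8.2.1.1 defines the FAS in two paragraphs that do not sit well together. The first takes in everyone enrolled and dosed at least once, adds that "The FAS will exclude subjects with major protocol violations", and makes the set primary for efficacy. The second says there will be two such sets, one per drug, and describes each only by receipt of at least one dose of that drug.

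The SAP carries no exclusion. The E/C/F/TAF set "will include all subjects who (1) were enrolled in the study and (2) received at least 1 dose of E/C/F/TAF study drug", and the B/F/TAF set "will include all subjects who (1) were enrolled in the study and (2) received at least 1 dose of B/F/TAF study drug". SAP 7.3 then states: "There are no changes from the protocol-specified efficacy analyses".

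On violations themselves, Protocol 6 requires that "The investigator must document any deviation from protocol procedures" in the source documents and eCRF. SAP 4.3 plans one listing, of subjects "who violated at least 1 inclusion or exclusion criterion". Neither document says which violations are major, who decides, or when.

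**The concern.** Read on its own, the exclusion sentence gives a different denominator from the SAP for the snapshot, missing-as-failure, missing-excluded and CD4 summaries. A reader holding the protocol would expect some treated subjects to be left out, whereas the SAP leaves out none and reports no departure.

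The sentence is also unsafe as written. Removing treated subjects on an undefined judgement in an open-label, single-arm study, where those judging can see the viral loads, could raise a response rate. In a set of about 50 subjects, each removal would show.

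**Working it through.** **1. Is the conflict between the two documents?** Only in part.

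| Source | Enrolled | Dosed | Major violators removed |
|---|---|---|---|
| Protocol 8.2.1.1, first paragraph | yes | yes | yes, term undefined |
| Protocol 8.2.1.1, second paragraph (both sets) | not stated | yes | not mentioned |
| SAP 3.1.3 and 3.1.4 | yes | yes | no |

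The SAP matches the protocol's second paragraph, which describes the two sets actually used. The exclusion sentence is the odd one out, within the protocol as well as against the SAP.

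**2. Was anyone removed from the E/C/F/TAF set?** The SAP's disposition mock (Appendix Table 1) has these counts already filled in: 75 screened − 15 screen failures − 5 eligible but not enrolled = 55 enrolled; 0 never treated; 55 in the safety set; 55 in the FAS.

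The interim results in Protocol 1.2.5 agree. At Week 24, 6 subjects (10.9%) had no data and 1.8% (1/55) had HIV-1 RNA of 50 copies/mL or more, leaving 55 − 6 − 1 = 48. At Week 48, 8 (14.5%) had no data and 3.6% (2/55) had 50 copies/mL or more, leaving 55 − 8 − 2 = 45.

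Exact (Clopper-Pearson) 95% limits for x/n are the 2.5% point of Beta(x, n − x + 1) and the 97.5% point of Beta(x + 1, n − x):

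| Result | x/n | Computed | Reported |
|---|---|---|---|
| Week 24 snapshot | 48/55 | 87.3% (75.5, 94.7) | same |
| Week 48 snapshot | 45/55 | 81.8% (69.1, 90.9) | same |
| Week 48, missing = failure | 46/55 | 83.6% (71.2, 92.2) | same |
| Week 48, missing excluded | 46/47 | 97.9% (88.7, 99.9) | same |

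Among all fractions with n from 20 to 200, each reported percentage with its interval is matched by that one fraction only. The primary safety result, 18/55 = 32.7%, has the same denominator of 55. No treated subject was left out of the reported E/C/F/TAF FAS.

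**3. What could the sentence have done?** This is an illustration, since no count of major violators is given. Take k subjects out of 45/55; the low end assumes all were responders, the high end that none were.

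- k = 1: 44/54 = 81.5% to 45/54 = 83.3%
- k = 2: 43/53 = 81.1% to 45/53 = 84.9%
- k = 5: 40/50 = 80.0% to 45/50 = 90.0%

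These shifts would come from applying the protocol sentence. Under the SAP, k = 0 and the rate stays at 81.8%.

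**4. What of the B/F/TAF set?** Its size is blank in the mock. At least 7 of the 55 had stopped study drug early by Week 48 (Protocol 1.2.5), and such subjects cannot enter the extension (Protocol 6.4.2), so the set holds at most 55 − 7 = 48, and one subject is at least 1/48 = 2.1% of it. The protocol names no B/F/TAF efficacy endpoint; its B/F/TAF objective is safety and tolerability. The by-visit HIV-1 RNA and CD4 summaries for that phase are descriptive additions in SAP 7.2.2, made on the dosed set.

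**The case for a change.** The strongest case for acting is that the text is wrong and correcting it costs almost nothing. The FAS is the primary efficacy set, an exclusion from it was dropped, and SAP 7.3 says nothing changed. A set of 55 out of 55 does not show whether there were no major violators or the rule was ignored. SAP 3.1 fixes membership before data finalization, but that supplies no criterion. The Week 24 and Week 48 snapshot results "were summarized as part of the Week 48 clinical study report and will not be repeated for the final analysis", so this SAP will not revisit them.

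Much of this stands. The sentence is unreconciled, the term is undefined, and SAP 7.3 would be more accurate with a line on it. The documents cannot settle why all 55 were kept.

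Two parts carry less weight. Calling it an undeclared departure overlooks the protocol's own second paragraph, which the SAP follows, and can in any case refer only to this final-analysis SAP, because no SAP for the earlier analyses is supplied. Nor does SAP 1 require a declaration in the study report. Its rule reads: "Any changes made to the analyses after the finalization of the SAP will be documented in the final clinical study report". The FAS definition is part of the finalized SAP, so it is not a later change.

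**Conclusion.** No change to the plan follows, because none would improve it. The SAP governs the final analysis and already counts every enrolled and dosed subject, which is the set one would choose. The hazard lies in a sentence that the SAP does not apply.

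The effect on the reported E/C/F/TAF results at Weeks 24 and 48 is nil: both rest on 55 of 55. The primary endpoint is unaffected, since Protocol 8.2.1.2 bases safety on all dosed subjects. The efficacy summaries are secondary or descriptive, with no formal testing (SAP 3.5), so no decision turns on the denominator.

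This rests on the final analysis following SAP 3.1.3 and 3.1.4 as written. Two things cannot be checked from the documents: the Week 96 result, from an analysis already done, and the B/F/TAF count, which is at most 48. A note in the study report that the exclusion was not applied would be tidy record-keeping, but it would alter neither what is analysed nor what can be concluded.
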